8.2.4 Relationship with Receipt of Test Article

The clinical investigator will assess all AEs for their relationship to the study agent using the following classifications:

- Definitely related: Clear-cut temporal association, with no other possible cause
- Probably related: Reasonable temporal association, and a potential alternative etiology is not apparent
- Possibly related: Less clear temporal association; other etiologies also possible
- Unlikely related: Temporal association between the AE and the study agent or the nature of the event is such that the study agent is not likely to have had any reasonable association with the observed illness/event (cause and effect relationship improbable but not impossible)
- Unrelated: The AE is completely independent of study agent administration, and/or evidence exists that the event is definitely related to another etiology

The degree of certainty with which an AE can be attributed to study agent administration will be determined by how well the event can be understood in terms of one or more of the following:

- A reaction of a similar nature having previously been observed with this type of vaccine and/or formulation or naturally occurring Zika illness
- The event having often been reported in the literature for similar types of vaccine products

All local injection-site reactions will be considered causally related to inoculation. Causality assessment is based on information available at the time of the AE assessment. The investigator may revise the causality assessment as additional information becomes available.

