- 1) Assess the frequency, quantity, and duration of viremia after a single dose of rZIKV/D4Δ30-713 given at either 10^3 PFU or 10^4 PFU.
- 2) Evaluate the number of vaccine recipients infected with either 10^3 PFU or 10^4 PFU rZIKV/D4Δ30-713. Infection is defined as recovery of infectious vaccine virus from the blood, serum, or urine of a subject and/or by seroconversion to ZIKV (plaque-reduction neutralization titer [PRNT₅₀] $\geq 1:10$) within the 90-day period following vaccination.
- 3) Determine the durability of antibody response 26 weeks after vaccination.
- 4) Determine the quantity and duration of ZIKV presence as determined by:
 - The peak virus titer in the blood and the duration of viremia induced by the LA Zika vaccine as determined by RT-PCR and virus culture
 - The quantity and duration of possible Zika vaccine shedding in urine determined by RT-PCR and virus culture
 - The quantity and duration of possible Zika vaccine shedding in vaginal secretions determined by RT-PCR and virus culture
 - The quantity and duration of possible Zika vaccine shedding in semen determined by RT-PCR and virus culture

Exploratory objectives:

- 1) To evaluate the phenotype of peripheral blood mononuclear cells (PBMCs) at primary infection with the rZIKV/D4Δ30-713 vaccine.
- 2) To evaluate the cellular immune response to primary infection with the rZIKV/D4Δ30-713 vaccine.
- 3) To evaluate the innate immune response to primary infection with the rZIKV/D4Δ30-713 vaccine.
- 4) To evaluate B and T cell memory responses following primary infection with the rZIKV/D4Δ30-713 vaccine.
- 5) To evaluate the antibody response in saliva to infection with rZIKV/D4Δ30-713 as a possible diagnostic tool. This will be done in a subset of subjects (those enrolled at the Center for Immunization Research [CIR]).

Primary Endpoints

Safety

Occurrence, intensity and relationship to vaccination of solicited local and general adverse events (AEs) within the 28-day follow-up period after vaccination.

Occurrence, intensity and relationship to vaccination of unsolicited AEs within the 28-day (Days 0-28) follow-up period after vaccination.

Occurrence of medically-attended adverse events and serious adverse events (SAEs) throughout the entire study period.

Immunogenicity

Determination of the peak neutralizing antibody titer to ZIKV through 90 days following vaccination with either 10^3 PFU or 10^4 PFU of rZIKV/D4 Δ 30.

Secondary Endpoint

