The subject, investigator, and clinical staff will not know which treatment group the subject has been assigned to. In addition, other personnel assigned to monitor the study will not know the treatment assignment of the subject. Clinical staff will remain blinded to treatment assignment until all subjects within a block of 7 subjects have reached study day 90. Once the time point for unblinding has occurred (study day 90 for subjects within a block), the principal investigator (PI) can request treatment assignments in writing from the unblinded study staff.

If it becomes necessary to unblind a specific subject's assignment for emergency medical management prior to all subjects within a block completing study day 90 post-vaccination, the PI will contact the unblinded study staff and obtain the treatment assignment of the subject in question. Only that specific subject's assignment will be unblinded. The sponsor, Office of Clinical Research Policy and Regulatory Operations (OCRPRO) and the DSMB executive secretary will be notified of the event within 2 business days. This will also be documented in the subject's study chart.

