8.1.3 Adverse Reaction

An adverse reaction (AR) is an AE that is caused by an investigational agent (drug or biologic). AEs that are deemed possibly, probably, or definitely related to study article will be classified as adverse reactions. ARs are categorized as solicited ARs and other ARs. Solicited ARs include local reactogenicity, systemic reactogenicity, and laboratory events. Solicited ARs are those events that the clinician is specifically evaluating during the 28-day post-inoculation period, listed in [Table 9](#). All AEs are evaluated using the Adverse Event Grading Table in Section [14.1](#), [Appendix 1](#).

Table 9: Solicited Adverse Events/Adverse Reactions

Systemic Reactogenicity	Laboratory Events	Local Reactogenicity
Fever	Decreased Hemoglobin	Injection Site Pain
Headache	Neutropenia	Injection Site Erythema
Retro-orbital Pain (ROP)	Elevated ALT	Injection Site Tenderness
Photophobia	Thrombocytopenia	Injection Site Induration
Nausea	Leukocytosis	Injection Site Pruritus
Fatigue		
Myalgia		
Arthralgia		
Non-purulent Conjunctivitis		
Muscle Weakness		
Zika Virus-Like Rash		

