8.1.5 Pregnancy

Pregnancy itself is not an AE. However, complications of pregnancies are AEs and may be serious adverse events (SAEs). Events that meet SAE criteria during pregnancy, delivery, or in the neonate (e.g., congenital anomaly/birth defect) are reportable to the Clinical Safety Office (CSO) per the sponsor's reporting guidelines. Pertinent obstetrical information for all

pregnancies will be reported to the CSO via the REDCap reporting system within 1 business day from site awareness of the pregnancy on the Pregnancy Notification and Outcome Form.

Pregnancy outcome data (e.g., delivery outcome, spontaneous or elective termination of the pregnancy) will be reported to the CSO within 3 business days of the site's awareness on a protocol-specified form. If a subject becomes pregnant within 28 days of test article administration, the subject will be unblinded to determine if she received ZIKV. If she did receive ZIKV, she will be referred to an OB/GYN experienced in caring for ZIKV-infected pregnant women ([name] at JHU).

If the pregnancy occurs prior to study day 28 after rZIKV/D4Δ30-713 administration, as determined by a positive pregnancy test at the study day 28 visit or before, the subject will not be included in the per-protocol analysis. The subject will remain on the study for safety follow-up.

- If unblinding the treatment assignment would help the subject determine whether she wishes to continue her pregnancy, her treatment assignment will be unblinded.
- The research subject will be advised to notify her obstetrician of study participation and study agent exposure.
- The pregnancy will be reported to the DSMB (if applicable) and/or IRB (if applicable).

If the pregnancy occurs after study day 28 following rZIKV/D4Δ30-713 administration, as determined by a positive pregnancy test after the study day 28 visit, the subject will be included in the per-protocol immunogenicity analysis.

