8.2 Assessment of Adverse Events

8.2.1 Identification of Adverse Events

All AEs occurring from the time the subject is enrolled (at administration of investigational agent on day 0) through the Study Day 28 will be documented, recorded, and reported. The Investigator will assess all AEs with respect to **Seriousness**, **Severity**, and **Causality** (relationship to study agent and relationship to research) according to the following guidelines. An assessment of safety will include clinical observations and monitoring of hematological, blood chemistry, and immunologic parameters. Safety will be evaluated by monitoring the subjects for local and systemic adverse events during the course of the trial. Subjects will be closely monitored for 30 minutes following inoculation. Additionally, subjects will return to the clinic on study days 4, 6, 8, 10, 12, 14, 16, 21, and 28 post-inoculation and may be asked to return more often if warranted. It is during this time period that we anticipate AEs related to infection with the vaccine virus to manifest themselves; therefore, the subjects will be seen frequently. Study staff will review subjects' reported temperatures and clinical temperatures for the first 16 days following inoculation to assess for AEs. At each visit through study day 28 following inoculation, subjects will be queried about adverse events, including possible vaccine-related AEs (solicited AEs) and will have a focused physical exam performed. A study clinician will be available to subjects by telephone or pager 24 hours a day during the study evaluation period.

All AEs will be recorded during the period after the subject receives the study vaccine through and including post-inoculation study day 28.

All SAEs will be assessed appropriately as AEs and reported following SAE reporting guidelines outlined in Section 8.3.2 of this protocol.

8.2.2 *Protocol Specific Adverse Event Definitions*

Fever: Temperature $\geq 100.4^{\circ}\text{F}$ lasting at least 1 hour

ZIKV-like Rash: Areas of **confluent** macular or maculo-papular rash over trunk and extremities, blanches when compressed.

Non-purulent conjunctivitis: Bilateral reddening of the sclera of the eyes without evidence of exudate or crusting of the eyelids

Headache: A pain located in the head, over the eyes, at the temples, or at the base of the skull.

ROP: Bilateral pain situated behind the orbits of the eye

Photophobia: An abnormal sensitivity or intolerance to light

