10.3 Safety Endpoint

The primary safety endpoint is the frequency of rZIKV/D4Δ30-713-related AEs, as classified by both severity and seriousness, through active and passive surveillance. Separate assessments of systemic and local reactions will be performed.

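### Causality calls behind the primary safety endpoint stay open to revision after unblinding, and the plan does not say which call is tabulated

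*Combined protocol and SAP*

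**What the plan says.** **Revision rule.** Section 8.2.4 says of the initial call: "Causality assessment is based on information available at the time of the AE assessment". It then adds: "The investigator may revise the causality assessment as additional information becomes available". It gives no time limit and no blinding condition.

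**Endpoint.** Section 10.3: "The primary safety endpoint is the frequency of rZIKV/D4Δ30-713-related AEs, as classified by both severity and seriousness". The Precis lists among its primary safety endpoints: "Occurrence, intensity and relationship to vaccination of unsolicited AEs within the 28-day (Days 0-28) follow-up period after vaccination". Section 8.1.3 gives the conversion rule: "AEs that are deemed possibly, probably, or definitely related to study article will be classified as adverse reactions".

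**Collection window.** Section 8.2.1: "All AEs will be recorded during the period after the subject receives the study vaccine through and including post-inoculation study day 28".

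**Unblinding.** Section 4.1.5 allows a block of seven to be unblinded to all staff when its last subject reaches Day 90. Section 4.1.6 adds that from then on "the principal investigator (PI) can request treatment assignments in writing from the unblinded study staff". Two routes are earlier and concern one subject at a time: emergency medical management (4.1.6) and early pregnancy (8.1.5: "If a subject becomes pregnant within 28 days of test article administration, the subject will be unblinded to determine if she received ZIKV"). Scheduled visits continue to Day 180.

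**Limits already in the plan.** Section 8.2.4 treats every local injection-site reaction as related, in both arms. Section 10.2 tabulates AEs as well as ARs, by group. Section 9.1 requires corrections in CRIMSON to be tracked by time, date, person and content.

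**The concern.** Section 4.1.6 gives protection of AE assessment from bias as the reason for double-blinding. Relatedness is the most subjective part of that assessment and decides whether an AE counts towards the Section 10.3 endpoint. The initial calls should be made blinded, because AE collection ends at Day 28 and planned unblinding comes no earlier than Day 90. The plan then leaves those stored calls open. It does not exclude the treatment assignment from the information that may prompt a revision, and it does not say whether the blinded or the latest call is tabulated.

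No misconduct is needed for this to matter. An investigator who learns that a subject received diluent may see a reason to move a possibly related headache to unrelated. One who learns that a subject received vaccine may move a call either way. If that happened, the AR rates would partly reflect knowledge of treatment. The issue is the stored Day 0-28 calls, not data collected after Day 90.

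**Working it through.** The point is procedural, so there is no power or alpha figure to reproduce. The check has three parts.

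**1. Is there a lock anywhere?** Sections 4.1.5, 4.1.6, 8.1.3, 8.2, 9.1 and 10.2 to 10.6 were read together. None freezes relatedness at Day 28, before block unblinding or at a database lock. None names the version to be analysed. The audit trail in 9.1 makes a change visible but neither prevents it nor selects the analysed value.

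**2. Timing.**
- End of AE collection to the earliest planned block unblinding: 90 − 28 = 62 nominal days, all blinded.
- Block unblinding to the final visit: 180 − 90 = 90 nominal days for the last subject in the block to reach Day 90, and fewer for the others.

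A blinded lock is therefore feasible, and without one the calls remain open while treatment is known.

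**3. Scale.** Each cohort has 20 vaccine and 8 placebo recipients (Table 1). One reclassified subject moves the AR rate by:
- placebo: 1/8 = 12.5 points
- vaccine: 1/20 = 5.0 points

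*Illustration from Table 7 (Cohort 1 headache).* The counts are 50.0% × 20 = 10 and 62.5% × 8 = 5. A one-sided Fisher exact test of 10/20 against 5/8 gives P = 0.8454, the printed value, which confirms the counts. Table 7 does not give relatedness by event. Assume that all 15 headaches were first called related:

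| Calls changed after unblinding | Vaccine | Placebo | Difference (vaccine − placebo) |
|---|---|---|---|
| None | 10/20 = 50% | 5/8 = 62.5% | −12.5 points |
| One placebo | 10/20 = 50% | 4/8 = 50% | 0 |
| All five placebo | 10/20 = 50% | 0/8 = 0% | +50 points |
| All ten vaccine | 0/20 = 0% | 5/8 = 62.5% | −62.5 points |

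The last two rows are the extremes of an assumed range, not an estimate. When only placebo calls change, the vaccine-arm related-AE rate stays at 50%. Only changes to vaccinees' calls move that rate.

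**The case against.** The strongest reply is that little depends on this, for five reasons.

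- **All-cause AEs are tabulated by arm.** A reader might infer that recoding placebo events would destroy the background rate. The documents do not support that. Changing relatedness deletes no event: the placebo headache rate stays 5/8 in the AE table, which is the comparison that the placebo group is there to provide (4.1.2). This stands.
- **The vaccine-arm rate need not move.** A reader might also infer that the vaccine would be made to look more reactogenic, by up to 50 points. That figure needs every placebo headache recoded and no vaccinee's. It concerns a between-arm AR difference that the plan does not prespecify, in a study that Section 10.2 calls descriptive. The opposite extreme is equally allowed, so no direction can be claimed. This stands too.
- **Recoding placebo events is not clearly licensed.** Section 4.1 counts placebo as test article, and the title of 8.2.4 refers to receipt of test article. Section 6.3, however, separates study agent from placebo. The reading is open, which is a reason to settle it.
- **Controls exist.** The initial calls are blinded, the halting rules need prompt causality judgments, changes are tracked, and monitors compare CRIMSON with source. Individual unblinding exposes one subject, not an arm. These controls make late changes detectable, but they do not settle which call is analysed.
- **Revision serves safety.** Causality should be updated when a diagnosis or result arrives. That is right, and a lock on the analysed value need not prevent it.

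A lock may exist in a document not supplied, such as the safety review and communications plan. If so, 8.2.4 and 10.3 should cite it.

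**Conclusion.** The gap is real and limited. A stated permission, with no cut-off at unblinding, lets unblinded judgment alter the relatedness calls that define the primary safety endpoint. It affects Day 0-28 systemic, laboratory and unsolicited AEs. It does not affect local injection-site reactions or all-cause AE frequencies.

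The firm measure of size is the leverage of one subject: 12.5 points in placebo and 5 points in vaccine, per cohort. The headache range of −62.5 to +50 points, against −12.5 with nothing recoded, rests on two assumptions that the documents cannot confirm: that all 15 events were first called related, and that one arm's calls were all changed. The possible consequence is bias in descriptive AR rates, in either direction, not an error in alpha or power. A reader should not infer that any call was changed, because nothing in the documents shows it. This is a cheap improvement.

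**What to change.** Add to Sections 8.2.4 and 10.3:

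- Severity, seriousness and relationship for all Day 0-28 AEs are finalised in CRIMSON before the block, or an individually unblinded subject, is unblinded.
- The primary AR tables use the last assessment made while blinded. For blocks already unblinded, that assessment is recovered from the audit trail.
- Later revisions are recorded with date, reason and blinding status, used for safety reporting, and listed separately from the primary tables.

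The cost is a few sentences and one data-lock step. No extra visits are needed, and the 62 nominal blinded days leave time for planned unblinding. Individual unblinding may come at short notice, so the rule should rely on the last blinded entry and must not delay access to the assignment. The downside is that a genuinely new diagnosis made after the lock appears only in the separate listing.

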8.2.5 Adverse Event Action Taken

The investigator/designee will assess the action taken by the subject or the study staff in relation to the AE, using the following classifications:

Action

- 1 = None
- 2 = Remedial therapy (more than 1 dose of medication required)
- 3 = Discontinued study
- 4 = Hospitalization
- 5 = Other

8.2.6 Adverse Event Outcome

The investigator/designee will assess the outcome of the AE, either at resolution or the end of the study period, using the following classifications:

Outcome

- 1 = Resolved
- 2 = Continuing
- 3 = Continuing Chronic Condition
- 4 = Unknown, Off-Study before could confirm resolution of AE
- 5 = Death
- 6 = Unknown

8.2.7 Adverse Event Seriousness

The investigator/designee will categorize all AEs as either serious or non-serious using the criteria defined in Section 8.1.6 of this protocol.

Any events defined as serious will also be reported following SAE reporting guidelines outlined in Section 8.3 of this protocol.

8.3 Adverse Event Reporting

8.3.1 Non-Serious Adverse Events

Non-serious AEs will be followed to resolution or until the study ends, and will be reported to the sponsor as requested, to the IRB according to IRB policies, to the DSMB as required, and to the FDA at least annually in the annual report.

AEs meeting the pausing criteria outlined in Section 8.5 of this protocol will be reported to the sponsor following the SAE reporting guidelines. AE data will be submitted to the IND Sponsor when requested for periodic safety assessments, review of IND annual reports, review of IND safety reports, and preparation of final study reports.

8.3.2 Serious Adverse Events

Office of Clinical Research Policy and Regulatory Operations Clinical Safety Office

All SAEs (regardless of relationship and whether or not they are also unanticipated problems) must be reported according to the sponsor's reporting plan by using the REDCap system. Deaths and immediately life-threatening SAEs must be reported to the CSO within 1 business day after the site becomes aware of the event. All other SAEs must be reported within 3 working days of notification of the SAE occurrence to:

- REDCap website: <https://crimsonredcap.cc.nih.gov/redcap/index.php>
- OCRPRO CSO [contact], [contact], E-mail: [contact]

SAEs that have not resolved by the end of the follow-up period are followed until final outcome is known. If it is not possible to obtain a final outcome for an SAE (e.g., the subject is lost to follow-up), the reason a final outcome could not be obtained will be recorded by the investigator on the AE case report form and according to the sponsor's reporting guidelines.

SAEs that occur after the study follow-up period (study day 180) that are reported to and are assessed by the investigator to be possibly, probably, or definitely related to study drug must be reported to the CSO.

Data and Safety Monitoring Board

All SAEs must be reported by telephone (followed by written report), email, or fax within 1 working day of notification of the SAE occurrence to:

- The DSMB executive secretary – [contact], [contact], Email: [contact]

Johns Hopkins University Biosafety Committee

All SAEs must be reported by telephone (followed by written report), email, or fax within 1 working day of notification of the SAE occurrence to:

- The JHU Institutional Biosafety Committee: [contact], [contact]

Institutional Review Board Reporting

All SAEs will be reported to WIRB-Copernicus Group, Inc (WCG IRB) and UVM IRB as per guidelines, respectively, for JHU and UVM as below:

- **WCG IRB Guidelines:**

WCG IRB [contact], [contact]
www.wcgirb.com for updated reporting guidelines

- **UVM IRB Guidelines:**

- Investigators are required to report AEs that fit the following criteria:
 - Report timelines are based on the time the investigator or site personnel becomes aware of them:
 - A local death report within 48 hours
 - All other local AEs should be reported promptly, not to exceed 7 days
- Local AEs (whether or not they are serious) that are unexpected, and possibly, probably, or definitely related to study participation:
 - **Local AE:** A negative side effect resulting from the study intervention that occurred to a subject enrolled at UVM or another research site under the jurisdiction of the UVM IRB.
 - **Unexpected:** An event does not meet the criteria of unexpected if it is (1) included in the current protocol, drug/device brochure, or the informed consent; or (2) due to the subject's underlying disease or predisposing risk factors
 - **Related:** An AE is considered to be related if there is a reasonable possibility that the event was caused by the protocol or study

interventions. A related event has a strong temporal relationship to the drug, device, or intervention, and an alternative cause is unlikely. If it cannot be determined whether an event is related, it should be reported as “possibly related.”

- At UVM, all SAEs must be reported to the UVM IRB according to UVM IRB guidelines.
- UVM IRB [contact], [contact]

